6.5 Scheduled Follow-ups

No follow-up visits or records are required for this study.

6.6 Description of activities performed by Sponsor Representatives

Trained sponsor personnel may perform certain activities to ensure compliance to the clinical investigational plan and may provide technical expertise.

Sponsor personnel will not:

- Perform the informed consent process
- Practice medicine

CIP

- Provide medical diagnosis or treatment to subject
- Discuss a subject's condition or treatment with a subject without the approval and presence of a health care practitioner
- Independently collect clinical study data
- Complete or sign study's Case report Forms

6.7 Subject study completion

When the subject's participation in the clinical study has been completed, the subject will return to the medical care as per physician's recommendation.

6.8 Any Known or Foreseeable Factors that May Compromise the Outcome of the Clinical Study or the Interpretation of the Results

All foreseeable factors that may compromise the outcome have been taken into account by clinical study design and well-defined subject selection criteria.

6.9 Criteria and Procedures for Subject Withdrawal or Discontinuation

Subjects must be informed about their right to withdraw from the study at any time and for any reason without sanction, penalty or loss of benefits to which the subject is otherwise entitled and withdrawal from the study will not jeopardize their future medical care or relationship with the investigator. Subjects will be asked to specify the reason for the withdrawal, but have the right not to answer.

The investigator may decide to withdraw a subject from the study at any time with reasonable rationale. The subject's future care will not be influenced by a decision, voluntary or otherwise, to withdraw from the study. All reasonable efforts should be made to retain the subject in the clinical study until completion of the study.

Reasons for subject's withdrawal include, but are not limited to:

- Subject refuses to continue participating in the study
- Subject does not meet the inclusion/exclusion criteria and does not require additional follow-up for safety reasons.
- Subject is deceased (cause must be documented)
- Subject's non-compliance
- Subject's participation is terminated by the PI or investigator, although the subject consented, since participation is no longer medically appropriate
- Subject's VA is not present or inducible before the ablation procedure

If a subject withdraws from the clinical study, the site will record the subject's reasons for withdrawal, on a Withdrawal CRF.

When subject withdrawal from the clinical study is due to an adverse event the subject will be followed until resolution of that adverse event or determination that the subject's condition is stable. The status of the subject's condition should be documented at the time of withdrawal.

CIP

7.0 COMPLIANCE TO CIP

7.1 Statements of Compliance

The study will be performed in accordance with the most current versions of the World Medical Association (WMA) Declaration of Helsinki, ISO14155 and any regional and/or national regulations and will be compliant to this International Standard and any regional and national regulations, as appropriate.

The investigator will not start enrolling subjects or requesting informed consent from any subject prior to obtaining IRB/EC approval and Competent Authority approval, if applicable, and authorization from the sponsor in writing for the study.

In case additional requirements are imposed by the IRB/EC or Competent Authority, those requirements will be followed, if appropriate. If any action is taken by an IRB/EC, and regulatory requirements with respect to the study, that information will be forwarded to St. Jude Medical.

As sponsor, St. Jude Medical has taken up general liability insurance in accordance with the requirements of the applicable local laws. Appropriate country representative will be utilized to understand the requirements for the type of insurance that will be provided for subjects, such information will be incorporated into the informed consent, as applicable.

If required, additional subject coverage or a study specific insurance will be provided by the Sponsor as well.

7.2 Adherence to the Clinical Investigation Plan

A deviation is defined as an event where the clinical investigator, site personnel, sponsor or sponsor representative did not conduct the clinical study according to the Clinical Investigational Plan, IRB/EC requirements or the Investigator Agreement. The investigator is not allowed to deviate from the CIP, except as specified under emergency circumstances.

In some cases, failure to comply with the CIP may be considered failure to protect the rights, safety and well-being of subjects, since the non-compliance exposes subjects to unreasonable risks. For example, failure to adhere to the inclusion/exclusion criteria: these criteria are specifically defined by the Sponsor to exclude subjects for whom the device is not beneficial and the use involves unreasonable risks. This may be considered failure to protect the rights, safety and well-being of the enrolled subject. Similarly, failure to perform safety assessments intended to detect adverse events may be considered failure to protect the rights, safety and well-being of the enrolled subject. Investigators should seek minimization of such risks by adhering to the CIP.

Simultaneously, in the event that adhering to the CIP might expose the subject to unreasonable risks, the investigator is also required to protect the rights, safety and well-being of the subject by intentionally deviating from the requirements of the CIP, so that subjects are not exposed to unreasonable risks.

CIP

It is the responsibility of the investigator to provide adequate medical care to a subject enrolled in a study.

Regulations require that the PI maintain accurate, complete, and current records, including documents showing the date of and reason for every deviation from the Clinical Investigational Plan. Relevant information for each deviation will be documented on a Deviation Case Report Form. The site will submit the CRF to St. Jude Medical.

Regulations require Investigators obtain approval from St. Jude Medical and the IRB/EC [as required] before initiating changes in or deviations from the protocol, except when necessary to protect the life or physical well-being of a subject in an emergency.

Prior approval must be requested when the PI anticipates, contemplates, or makes a conscious decision to depart from the CIP, except when unforeseen circumstances are beyond the investigator's control (e.g. a subject who fails to attend a scheduled follow-up visit, a subject is too ill to perform a CIP-required test, etc.). All deviations, including those beyond the investigator's control, must be reported on a CRF.

To obtain approval, the Principal Investigator may call or email and discuss the potential deviation with St. Jude Medical or designee prior to initiating any changes.

All deviations must be reported to appropriate regulatory authorities in specified timelines (if appropriate).

7.3 Repeated and serious non-compliance

In the event of repeated non-compliance or a one-time serious non-compliance, as determined by the Sponsor, a Clinical Research Associate or clinical representative will attempt to secure compliance by one or more of the following actions:

- Visiting the investigator
- Contacting the investigator by telephone
- Contacting the investigator in writing
- Retraining of the investigator

If an investigator is found to be repeatedly non-compliant with the signed agreement, the CIP or any other conditions of the clinical study, the Sponsor will either secure compliance or, at its sole discretion, terminate the investigator's participation in the clinical study.

8.0 ADVERSE EVENT

8.1 Definitions

Medical device

Any instrument, apparatus, implement, machine, appliance, implant, software, material or other similar or related article

CIP

- Intended by the manufacturer to be used, alone or in combination, for human beings for one or more of the specific purpose(s) of
 - Diagnosis, prevention, monitoring, treatments or alleviation of disease,
 - Diagnosis, monitoring, treatment, alleviation of, or compensation for, an injury,
 - Investigation, replacement, modification, or support of the anatomy or of a physiological process,
 - Supporting or sustaining life,
 - Control of conception,
 - Disinfection of medical devices and
- Which does not achieve its primary intended action in or on the human body by pharmacological, immunological or metabolic means, but which may be assisted in its intended function by such means

Adverse Event (AE)

Any untoward medical occurrence, unintended disease or injury, or untoward clinical signs (including abnormal laboratory findings) in subjects, users or other persons, whether or not related to the investigational medical device under study.

This definition includes events related to the investigational medical device or the comparator.
This definition includes events related to the procedures involved.

Serious Adverse Event (SAE)

An adverse event that led to:

- Death
 - A serious deterioration in the health of the subject, that either resulted in:
 - A life-threatening illness or injury OR
 - A permanent impairment to a body structure or a body function OR
 - An in-patient or prolonged hospitalization OR
 - A medical or surgical intervention to prevent life-threatening illness or injury or permanent impairment to a body structure or a body OR
 - Fetal distress, fetal death or a congenital abnormality or birth defect
- A planned hospitalization for a pre-existing condition, or a procedure required by the CIP is not considered a serious adverse event.

Adverse Device Effect (ADE)

An adverse event related to the use of an investigational medical device.

This definition includes adverse events resulting from insufficient or inadequate instructions for use, deployment, implantation, installation, or operation, or any malfunction of the investigational medical device.

CIP

This definition includes any event resulting from the use error or from intentional misuse of the investigational medical device.

Serious Adverse Device Effect (SADE)

Adverse device effect that has resulted in any of the consequences characteristic of a serious adverse event.

8.2 Procedure for assessing, recording and reporting adverse events

Safety surveillance within this study and the safety reporting both performed by the investigator, starts as soon as the subject is enrolled in this study (date of signature of the informed consent). The safety surveillance and the safety reporting will continue until the last investigational visit has been performed, the subject is deceased, the subject/investigator concludes his participation into the study or the subject/investigator withdraws the subject from the study, except as otherwise specified in the CIP.

All adverse event data including deaths will be collected throughout the clinical study by the investigator and reported to the Sponsor on a dedicated CRF.

Records relating to the subject’s subsequent medical course must be maintained and submitted (as applicable) to the Sponsor until the event has subsided or, in case of permanent impairment, until the event stabilizes and the overall clinical outcome has been ascertained. Adverse events will be monitored until they are adequately resolved. The status of the subject’s condition should be documented at each visit.

The investigator will report the event to the IRB/EC per their reporting requirements.

Reportable events to sponsor are considered:

- All Serious Adverse Events whether or not device/procedure related (SAEs and SADEs)
- Adverse Device Effects (ADE) Note: ADEs include procedure related events as well.
- Death events

All above events will be reported to the Sponsor, as soon as possible, but no later than 72 hours of first learning of the event.

The Sponsor will ensure that all events are reported to the relevant authorities as per regulations.

Should an AE occur, the investigator is requested to record AE information in the hospital records, document the information into the Adverse Event CRF according to the timelines mentioned above. Refer to Table 2 “Case Report Forms”.

Additional information such as clinic notes or other forms of medical records may be requested, when required, by the Sponsor in order to support the appropriate classification of the AEs and reporting of AEs to regulatory authorities.

CIP

The investigator must notify the IRB/EC, if appropriate, in accordance with national and local laws and regulations, of the AEs reported to the Sponsor.

All adverse events will be reported as per applicable regulatory requirements.

8.3 Subject Death

Procedure for recording and reporting subject death

All subject deaths are to be documented and reported to the sponsor within 72 hours after becoming aware of the event.

Should a death event occur, the investigator is requested to record death information in the hospital records, immediately document the information on the Death CRF and submit it to SJM. All subject deaths are to be documented and reported to the sponsor within 3 days after becoming aware of the event.

In order for the data related to deaths to be appropriately analyzed and adjudicated, the investigator is required to provide SJM with the appropriate source documentation of the death such as clinic notes or other forms of medical records.

A pre-procedure death is defined as death occurs before the start of the ablation procedure. A peri-procedure death is defined as death occurs after the start but on the day of the ablation procedure. A post-procedure death is defined as death occurs after the day of the ablation procedure.

An Adverse Event CRF should be completed in addition to the Patient Death CRF only if the patient death is associated with an adverse event. Otherwise, if there are no AEs associated with death, the completion of Patient Death CRF is sufficient.

The patient's death is an Early Conclusion of the subject's participation in the study. Therefore, beside completion of a Death CRF, the investigator is required to complete the Withdrawal form.

The investigator must notify the EC / IRB, if appropriate, in accordance with national and local laws and regulations.

8.4 COMPLAINT

Complaints are defined as an inadequacy of a medical device with respect to its identity, quality, durability, reliability, safety or performance. These include malfunctions, use errors and inadequate labeling.

Complaint reporting to sponsor: As this is a trial utilizing a market-released product, the investigator should notify the SJM Postmarket Surveillance Department by emailing the information about the complaint to the local country office or to: [contact] or calling [name]. Please contact the local SJM representative for any questions regarding the complaint reporting.

CIP

9.0 DATA MANAGEMENT

Overall, the Sponsor will be responsible for the data handling.

The sponsor and/or its affiliates will be responsible for compiling and submitting all required reports to governmental agencies.

Data will be analyzed by the Sponsor and may be transferred to the Sponsor’s locations outside of China and/or any other worldwide regulatory authority in support of a market-approval application.

St. Jude Medical respects and protects personally identifiable information that we collect or maintain. As part of our commitment, St. Jude Medical is certified to the U.S. - European Union Framework and U.S. – Swiss Safe Harbor Framework Agreements regarding human resources and subject clinical trial personal information. The privacy of each subject and confidentiality of his/her information will be preserved in reports and when publishing any data. Confidentiality of data will be observed by all parties involved at all times throughout the clinical study. All data will be secured against unauthorized access.

The Principal Investigator or institution will provide direct access to source data during and after the clinical study for monitoring, audits, IRB/EC review and regulatory authority inspections. As required, the Principal Investigator or institution will obtain permission for direct access to source documents from the subject, hospital administration and national regulatory authorities before starting the clinical study.

9.1 Data Management Plan

CRF data will be captured in a validated electronic database management Oracle Clinical system hosted by St. Jude Medical. All received data for the study will be entered by trained and qualified St. Jude Medical personnel. An electronic audit trail will be used to track any subsequent changes of the entered data.

9.2 Document and data control

Traceability of documents and data

The investigator shall ensure accuracy, completeness, legibility and timeliness of the data reported to the sponsor on the CRFs and in all required reports. Where copies of the original source document as well as print outs of original electronic source documents are retained, these shall be signed and dated by a member of the investigation site team with a statement that it is a true reproduction of the original source document.

Recording data

Source documents will be created and maintained by the investigational site team throughout the clinical study. The data reported on the CRFs will be derived from, and be consistent with, these source documents, and any discrepancies will be explained in writing.

CIP

The CRFs will be signed and dated by the authorized site personnel. Any change or correction to data reported on a paper CRF will be dated, initialed and explained if necessary, and will not obscure the original entry.

Review of data

The clinical investigation will be monitored by reviewing the CRFs approved by the investigators.

The following activities will occur:

- All CRFs will be reviewed for completeness and accuracy after uploading into the database.
- The investigator (co-investigator) and/or delegate is notified regarding any missing or unclear/inconsistent data.

10.0 REGULATORY INSPECTIONS

The investigator and/or delegate should contact St. Jude Medical immediately upon notification of a governmental agency inspection at the site. A clinical monitor or designee will assist the investigator and/or delegate in preparing for the audit.

An investigator who has authority to grant access will permit authorized governmental agency employees, at reasonable times and in reasonable manner, to enter and inspect any establishment where devices are held (including any establishment where devices are used or where records or results are kept).

An investigator, or any person acting on behalf of such a person with respect to the study, will permit authorized governmental agency employees, at reasonable times and in reasonable manner, to inspect and copy all records relating to the study.

An investigator will permit authorized governmental agency employees to inspect and copy records that identify subjects, upon notice that governmental agency has reason to suspect that adequate informed consent was not obtained, or that reports required to be submitted by the investigator, to the Sponsor or IRB/EC have not been submitted or are incomplete, inaccurate, false or misleading.

11.0 STATISTICAL CONSIDERATIONS

11.1 Statistical design, hypotheses, method and analytical procedures

This study is an acute, prospective, non-randomized, feasibility study.

11.2 Sample size

This feasibility study is expected to be conducted in the Fuwai Hospital, Beijing, China. It is designed to investigate 20 subjects meeting the inclusion criteria. As a feasibility study, there is no statistical-based sample size. Because this study does not require follow-up visits, attrition (i.e. incomplete data set due to deviation from protocol) is anticipated to be low - in approximately 5% of patients. In case of substantial drop-out rate (more than 10%), an increase in population will be conducted by amendment.

CIP

11.3 The provision for an interim analysis, when applicable

An interim analysis may be conducted when the enrollment total count is greater than 10.

11.4 The treatment of missing, unused or spurious data, including drop-outs and withdrawals

In case when a drop-out or withdrawals occurs, the subject's data will not be included in the study result analysis.

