4.5 Inclusion and Exclusion Criteria

A subject, who meets all of the inclusion criteria, and none of the exclusion criteria, is eligible to participate in this study.

All subjects enrolled in the clinical study (including those withdrawn from the clinical study or lost to follow-up) will be accounted for and documented, assigning an identification code linked to their names, alternative identification or contact information.

This log will be kept up to date throughout the clinical study by the principal investigator or his/her authorized designee. To ensure subject privacy and confidentiality of data this log must be maintained throughout the clinical study at the clinical site.

To participate in this clinical subject, the subject must meet all of the following inclusion criteria:

Inclusion Criteria

Subjects are eligible for clinical study participation if they meet all of the following inclusion criteria:

- Patients scheduled to undergo ablation for idiopathic OTVA
- Have the ability to provide informed consent for study participation.

Exclusion Criteria

Patients will be excluded from the study if they meet any of the following exclusion criteria:

- Be currently participating in any other investigational studies
- Be less than 18 years of age
- Be pregnant
- Has any other conditions that are not suitable for catheter ablation (including but are not limited to active whole-body infection or sepsis, coagulation or hemorrhage disorder history)

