6.4 Ablation Procedure Visit

In case the patient's VA is not present and cannot be induced before the ablation procedure, the ablation should not be performed according to the 2009 EHRA/HRS Expert Consensus on Catheter Ablation of Ventricular Arrhythmias¹. The following actions will be taken:

- Inform the subject about the withdrawal.
- Complete the Withdrawal CRF. The form must be authorized / approved by the principal or delegated investigator

The ablation procedure will be performed according to the Fuwai hospital's standard practice. During the ablation procedure, any clinical adverse events or protocol deviations are to be noted on the appropriate forms. The following information will be collected at the ablation procedure visit:

- Date of procedure

CIP

- The unipolar EGM, the bipolar EGM pairs as defined below, and the 12-lead surface ECG.
- Nonsuccessful and successful ablation sites tagged on the map.
- Acute success rate
- Indicate model and number of mapping and ablation catheters used in the procedure
- Adverse Events, Death, and/or Protocol Deviation notification (if applicable)

Mapping and EGM Recording

A quadripolar ablation catheter will be used to map the target site. Specifically, the unipolar EGM is recorded from the distal electrode (M1) of the mapping catheter and filtered at 0.5~100Hz. The bipolar EGMs are recorded from the distal (M1-M2), mid (M2-M3), and proximal (M3-M4) electrode pairs of the mapping catheter, respectively, and filtered at 30~500Hz. LAT is measured using the distal electrode pair and is defined as the interval between the initial sharp peak of the EGM and the onset of the VA QRS. The presence of the bi-RP is evaluated between the distal and mid electrode pairs and is defined as a rapid simultaneous deflection in the opposite direction of the initial part of the bipolar EGM occurring before the onset of the VA QRS. All the unipolar EGM, bipolar EGMs, and the 12-lead surface ECG will be displayed on the monitor for the physician’s reference and stored on the electrophysiology recording system and on the Ensite Velocity mapping system for off-line analysis. To guarantee accurate electroanatomic activation mapping and to avoid annotation of catheter-induced premature ventricular contractions (PVCs), the VA QRS morphology of each acquired mapping point will be compared to a 12-lead QRS template of the clinical arrhythmia.

Ablation

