Radiofrequency energy will be applied at 30W with a maximum temperature of 55 °C for regular ablation catheter, and 35 to 40W with a maximum temperature of 43 °C for irrigated ablation catheter. If the VA is not abolished within 10 seconds of RF ablation, the energy application will be terminated and the ablation site will be tagged as a nonsuccessful site on the map. If the VA is abolished within 10 seconds, the energy application will be continued for a total of 90 seconds and the site will be tagged as a successful site on the map. The procedure endpoint is reached when the targeted VA did not occur spontaneously after a waiting period of 30 minutes and could not be induced by electrical programmed stimulation before and after isoproterenol infusion and Valsalva maneuver.

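### Section 11.4 drops all data of any withdrawn subject, with no exception for ablation-site data already complete at withdrawal (minor)

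*Combined protocol and SAP*

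**What the plan says.** Section 11.4 is a single sentence. When a subject drops out or is withdrawn, that subject's "data will not be included in the study result analysis". It does not distinguish by reason, by timing, or by whether the data are complete, and no other section adds an exception.

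The data behind the primary endpoint come from one visit. Under 6.4 the unipolar and bipolar electrograms are stored during the procedure, and the items collected include "Nonsuccessful and successful ablation sites tagged on the map". The tag depends on whether the arrhythmia is abolished within 10 seconds of energy delivery; if it is, energy continues to 90 seconds in total and "the site will be tagged as a successful site on the map". Section 6.5 requires no follow-up.

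Section 11.2 says that "attrition (i.e. incomplete data set due to deviation from protocol) is anticipated to be low", at about 5% of patients, and adds: "In case of substantial drop-out rate (more than 10%), an increase in population will be conducted by amendment".

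Section 6.9 lists the withdrawal reasons, and 8.3 requires the Withdrawal form for any death.

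**The concern.** The primary endpoint is the predictive value of bi-RP and uni-QS for successful ablation. What an analysis needs from each site is the electrogram and the outcome. Both exist once the site has been tagged, and nothing that happens to the subject later makes that pair less valid.

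Section 11.4 nevertheless ties inclusion to the subject's final status. A subject who completes mapping and ablation and is then withdrawn loses every site from the analysis. The electrograms are displayed to the physician during the procedure and the tag is set at once, so such an exclusion would follow from an event or decision that comes after marker and outcome are known. In a study of about 20 subjects, each one counts.

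**Working it through.** **Inputs.** Planned sample 20, expected attrition about 5%, amendment trigger above 10% (all 11.2); exclusion rule (11.4); timing of data (6.4, 6.5); withdrawal routes (6.3, 6.9, 8.3). Section 11.2 states that the 20 has no statistical basis, so there is no sample-size figure to reproduce.

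**Step 1. Can withdrawal follow complete site data?** The routes, taken in turn:

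| Route | Can tagged sites exist already? |
|---|---|
| Arrhythmia absent and not inducible (6.4, 6.9) | No. Where the "VA is not present and cannot be induced before the ablation procedure, the ablation should not be performed" |
| Found ineligible (6.3, 6.9) | Yes; 6.3 covers the case where a study procedure has occurred. Exclusion from the main analysis is defensible on other grounds |
| Death (6.9, 8.3) | Yes; 8.3 defines deaths on the procedure day after its start, and after that day |
| Adverse event (6.9) | Yes, if the event occurs during or after ablation |
| Subject's own decision (6.9) | Yes; allowed at any time |
| Investigator's decision (6.9) | Yes; allowed at any time, given a reasonable rationale |
| Non-compliance (6.9) | Unlikely; no subject task after the procedure is described |

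The routes where the rule costs valid data are therefore death, adverse event, and a late decision by the subject or investigator.

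**Step 2. Compare 11.2 with 11.4.** Attrition in 11.2 is an incomplete data set due to a protocol deviation. A subject withdrawn after all sites are tagged has a complete data set, so is not attrition under 11.2 but is excluded under 11.4. The 5% figure therefore cannot serve as a rate for the withdrawals at issue here.

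**Step 3. Size per subject.** Share lost = number withdrawn / 20.

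- 1/20 = 5%
- 2/20 = 10%, which is not more than 10%, so 11.2 does not respond
- 3/20 = 15%, the first count above the trigger

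The anticipated attrition is 20 × 0.05 = 1 subject, but of the incomplete-data kind. The documents give no number for late withdrawals with complete data. It may be 0.

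**Step 4. Can the effect on a predictive value be computed?** No. The denominator of a positive predictive value is the number of marker-positive units, and the documents do not give it. To show the dependence only, assume one count per subject, M marker-positive subjects and x successes. Dropping a failure moves the value by x/[M(M−1)]. Dropping a success moves it by −(M−x)/[M(M−1)]. The largest absolute move is 1/M, reached only at x = M−1 or x = 1 respectively. For assumed M of 5, 8, 10 and 15 that ceiling is 20, 12.5, 10 and 6.7 percentage points. A less extreme assumed case: 6/8 = 75.0% becomes 6/7 = 85.7% if a failure is dropped, or 5/7 = 71.4% if a success is dropped. These numbers illustrate sensitivity to an unknown count; they do not estimate harm.

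**The case against.** The best case for leaving 11.4 alone is that it will hardly ever bite. There is one procedure visit and no follow-up, safety surveillance normally ends with the last study visit (8.2), and little time remains after tagging in which to withdraw. Non-inducible subjects have no sites to lose. Ineligible subjects, and those who revoke consent to data use, would stay out of the main analysis in any case. This is a feasibility study with no statistically based sample size, and a simple exclusion rule stated in advance has merit. All of this stands and sets the severity. It does not empty the set: 8.3 itself provides for death after the procedure day and treats it as a withdrawal.

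It might be said that 4.5 covers the point: "All subjects enrolled in the clinical study (including those withdrawn from the clinical study or lost to follow-up) will be accounted for and documented". That concerns a subject log and does not return anyone's data to the analysis.

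It might also be said that a tag is not final until the procedure is finished, since "The procedure endpoint is reached when the targeted VA did not occur spontaneously after a waiting period of 30 minutes" and the arrhythmia can no longer be induced. But 6.4 sets the site tag by the response to energy delivery, separately from the procedure endpoint, so a later withdrawal does not undo it.

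Three stronger readings are tempting and are not supported:

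- *That valid data will certainly be lost.* Loss depends on a withdrawal after tagging, and no rate is given.
- *That the results will be biased, or that an investigator could freely remove unfavourable cases.* Section 6.9 requires a reasonable rationale, asks for reasonable efforts to retain subjects, and has the reason recorded on the Withdrawal CRF. Nothing shows that late withdrawal would relate to marker or outcome.
- *That safety information is lost.* Adverse events and deaths are collected and reported under 8.2 and 8.3 whatever 11.4 says.

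**Conclusion.** The point holds in a limited form and is minor. As written, 11.4 removes complete electrogram and outcome data from the primary analysis if a subject is withdrawn after ablation, and it does not match the description of attrition in 11.2. Each affected subject costs 5% of the planned 20, together with all of that subject's sites. The number affected may be zero.

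This rests on reading 11.4 literally, on taking the site tag in 6.4 as the outcome, and on applying the analysis exclusion to the predictive-value analysis, since the plan does not define which analysis 11.4 covers. Outcome-related bias is possible but not shown, and no shift in a predictive value can be derived from the documents.

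**What to change.** Replace 11.4 with:

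> Ablation sites with an EGM and an outcome tag recorded before withdrawal are included in the predictive-value analysis, provided the subject has not revoked consent to use of the data. Data of subjects who revoke that consent are not used. Sites of subjects found ineligible after the procedure are excluded from the main analysis and reported separately. The number of withdrawn subjects and the reasons are reported.

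Before adopting it, check the wording against the data-use terms of the consent form, which Appendix D places under separate cover.

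The cost is four sentences and slightly more analysis work. Electrograms and tags are already collected under 6.4, and withdrawal reasons under 6.9. No procedure or visit changes.
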